3 INTRODUCTION AND RATIONALE

Multiple sclerosis (MS) is an autoimmune disease of the central nervous system characterised by relapses and progressive disability. The treatment of Relapsing-Remitting Multiple Sclerosis (RRMS) is based on therapies capable of modifying its natural course (disease-modifying therapies- DMTs); first-line therapies include interferon beta-1a (IFN β -1a), IFN β -1b and glatiramer acetate (GA) (Galetta et al., 2002).

The most frequent side effect of IFN β is flu-like syndrome (FLS) which includes myalgia, muscle weakness, chills and fever (Galetta and Markowitz 2005). Symptoms generally begin 3-6 hours after the injection and resolve within 24 hours. FLS, generally present in the first few months of therapy (Mohr et al., 1998), is the most frequent reason for discontinuing the treatment (Tremlett and Oger 2003).

A strategy to reduce the frequency and intensity of FLS is dose titration when IFN β treatment is started (Brandes et al., 2007). Low doses of steroids, paracetamol and non-steroidal anti-inflammatory drugs (NSAIDs) such as ibuprofen have proven to be effective in reducing the frequency and symptoms of FLS (Rio et al., 1998, Rice et al., 1999, Reess et al., 2002, Rio et al., 2004).

Despite these strategies, FLS persists at unacceptable levels in some patients and it becomes necessary to discontinue the therapy (Tremlett and Oger 2003). Management of FLS is therefore considered to be an unmet clinical need.

The pathogenesis of the symptoms needs to be understood in order to try to further reduce the impact of FLS thereby allowing the patient to continue the therapy and optimize its effectiveness. FLS appears to be linked to increases in endogenous pyrogens such as Interleukin 6 (IL-6) and Tumour Necrosis Factor-alpha (TNF- α) (Roth et al., 1997). An increase in IL-6 levels has been observed in patients who develop FLS during the first weeks of therapy; the increase is lower in patients treated with low doses of oral steroids (Martinez-Caceres et al., 1998, Rio et al., 2004). Moreover, a stimulation study with IFN β -1b has shown that the leukocytes of patients who develop fever as a result of therapy generally produce more interleukin-6 in vitro following a stimulation study with IFN β . (Montalban et al., 2000).

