5.2 Rationale behind the study design

Flu-like symptoms are largely subjective, and symptoms such as muscle pain, chills and a state of exhaustion may be associated with significant subjective variability which, combined with a different response to therapy, can create a confounding effect that is difficult to distinguish from the effect of the drug and the placebo.

Under these conditions, adopting an experimental parallel-arm design would entail an excessively large sample of subjects in order to have sufficient statistical power.

The advantage of a crossover approach lies in a smaller sample size, as every subject is exposed to a period of placebo treatment as well as a period of treatment with the study drug in a randomised sequence. Therefore each patient contributes to the sample size for more than one treatment, and the variability of intra-subject measurements is smaller than that between different subjects, revealing more clearly the difference between the drug and the placebo.

A crossover design is a type of randomised clinical trial in which N experimental units are divided into 2 groups: those randomly assigned to the first group receive the placebo and then the antihistamine; those randomised to the second group receive the antihistamine first and then the placebo. Each time interval in which one of the two treatments is administered is called a period.

In crossover designs in which two active drugs are compared, a suitable wash out time needs to be introduced between the end of one treatment and the start of the next to avoid carrying over the effect of one treatment into the next period.

On the other hand, when one of the two treatments is a placebo, this interval is not introduced as the wash out would simply lengthen the placebo treatment time. In this case the passage from one treatment to the other can occur without any interruption.

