10.2 Sample size

The severity of the FLS expressed as the patient's judgement on a VAS ranging between 0 and 10 is the parameter used to calculate the sample.

The clinical hypothesis is that four hours after administering IFN β , the average difference (d) of the VAS score between the two treatments is equal to or greater than 0.50, where d is expressed in standardized units.

Where $\mu_{Cetir.}$ is the mean VAS score obtained after administration of the standard therapy (SOT) plus cetirizine, and $\mu_{NoCetir}$ is the mean obtained after administration of the standard therapy alone (SOT), the difference between the two treatments will be expressed as:

$$d = \left| \mu_{\text{noCetir.}} - \mu_{\text{Cetir.}} \right| / \sigma = 0.50$$

where d is the effect size expressed in standard units and σ is the standard deviation of the difference.

Therefore the null hypothesis (two tailed) is

H0: $\left| \mu_{\text{noCetir.}} - \mu_{\text{Cetir.}} \right| / \sigma \leq 0.50 - \text{ or d=0}$;

While the alternative hypothesis is

Ha: $|\mu_{\text{noCetir.}} - \mu_{\text{Cetir.}}|/\sigma| > 0.50 - \text{ or } d \neq 0.$

Selecting * = 0.05 and β = 0.20 (power =80%), it is necessary to enrol 34 patients, who will be sequentially treated in accordance with a crossover design, as shown in the randomisation list.

Taking into consideration the possibility of a 15-20% drop-out rate, the sample to be randomised for the two sequences will be made up of 40 subjects.

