10.3.4 Efficacy

The efficacy of Cetirizine in reducing FLS symptoms in patients with RRMS being treated with IFN β will be evaluated 4 hours after IFN β administration (after 4 weeks of therapy within each sequence)

The VAS and FLS-S score variables will be analysed using analysis of variance (ANOVA) with repeated measurements. In accordance with the crossover design of the study, the carry-over effect and the sequence effect will be evaluated in addition to the treatment effect.

During the treatment, the severity of the FLS, evaluated using both the VAS and FLS-S scores and recorded 4 and 12 hours after the injection, will be analysed using analysis of variance with repeated measurements. In accordance with the crossover design of the study, the carry-over effect and the sequence effect will be evaluated in addition to the treatment effect.

Moreover, appropriate multiple comparisons will be made to evaluate the time of the treatment between and within groups.

The same analysis in line with the crossover design will be performed on the values of the area under the curve (AUC) of the mean VAS and FLS-S values, recorded 4 and 12 hours after the injection for each treatment.

Lastly, the severity scores for flu-like syndrome (FLS-S) will be compared with the baseline scores. The patients for whom the score is increased by 2 or more units will be defined as positive for FLS and their frequencies will be analysed using the Armitage method, according to the crossover design.

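### The efficacy ANOVA lists carry-over and sequence as two effects, which this two-period crossover cannot separate once period is fitted, and it does not name period

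*Protocol*

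**What the plan says.** Section 5.2 describes an AB/BA crossover: "those randomly assigned to the first group receive the placebo and then the antihistamine", and the second group takes them in the opposite order. It defines the time factor: "Each time interval in which one of the two treatments is administered is called a period". There is no washout, because with placebo as one of the treatments "this interval is not introduced as the wash out would simply lengthen the placebo treatment time".

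Section 10.3.4 gives the analysis: "The VAS and FLS-S score variables will be analysed using analysis of variance (ANOVA) with repeated measurements". It then says that "the carry-over effect and the sequence effect will be evaluated in addition to the treatment effect", first for the evaluation placed after four weeks of treatment and again for the scores recorded during treatment. No period effect is named there or elsewhere in section 10. No rule says what follows if a carry-over effect is found.

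Section 3 describes the syndrome as early in the course of interferon: "FLS, generally present in the first few months of therapy". Section 6.1 admits patients from three months of interferon onward, with no upper limit.

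**The concern.** The design has four sequence-by-period cell means. They support an overall level and three contrasts: treatment, period and sequence. Section 10.3.4 promises two results, carry-over and sequence, where the design gives one. It leaves out period, which can be estimated and which the treatment comparison needs if symptoms drift between the first and second four weeks.

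At stake is the treatment comparison itself. Without a period term, a drift enters the residual variance. It can also enter the treatment estimate, either when drop-out leaves the sequences unequal or when the three named effects are fitted as written. In addition, a report that shows carry-over and sequence as separate findings would claim a distinction the data cannot make.

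**Working it through.** **Inputs.** From section 10.2: d = 0.50 in units of the SD of the within-patient difference, two-sided alpha 0.05, power 80%, 34 evaluable, 40 randomised. From sections 1 and 5.2: two sequences of 20, two periods, no washout. Assumed, because the protocol gives no value: the period shift pi (period 2 minus period 1, in the same SD units), the between-period correlation rho, and the carry-over size lambda.

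**Planned size.** A paired t test at d = 0.50 has power 79.5% at n = 33 and 80.8% at n = 34, so 34 is reproduced. For drop-out, 34/0.85 = 40.

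**Aliasing.** Code the four cells with columns for intercept, sequence, period and treatment: the rank is 4. Add a carry-over column for placebo after cetirizine: there are 5 columns and the rank is still 4. Carry-over therefore adds nothing once the other terms are fitted.

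**The three named effects fitted literally, without period.** With carry-over coded only in the cell after cetirizine, the fit has rank 4 and solves as:
- treatment = (period 2 - period 1) in the placebo-first sequence alone
- sequence = (period 1 of cetirizine-first) - (period 2 of placebo-first)
- carry-over = the sum over both sequences of (period 2 - period 1)

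A pure period shift of 1 then gives treatment +1, sequence -1 and carry-over +2. With carry-over coded symmetrically (opposite signs in the two second-period cells), it equals half of sequence minus treatment under ±1 coding. The rank is then 3 of 4 and the model cannot be fitted.

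**Treatment without carry-over or period, 17 + 17.** The cetirizine-minus-placebo difference is tau + pi in the placebo-first sequence and tau - pi in the other (tau is the treatment effect). The shift cancels from the mean, but the SD of the differences grows by about sqrt(1 + pi²). Simulation with 40,000 runs per setting gives:

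| Shift pi | SD factor | Power, period omitted | Type I error, period omitted |
|---|---|---|---|
| 0.25 | 1.03 | 78.7% | 4.4% |
| 0.50 | 1.12 | 73.8% | 3.0% |
| 0.75 | 1.25 | 64.1% | 1.5% |

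With period in the model (32 degrees of freedom), power is 80.7% whatever the shift.

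**Unequal sequences, period omitted.** Bias = pi × (n1 - n2)/(n1 + n2), where n1 and n2 are the evaluable placebo-first and cetirizine-first patients. At 19 versus 15 this is 4/34 = 0.12 × pi, or about 0.03, 0.06 and 0.09 SD at the three shifts. At 20 versus 14 it is 6/34 = 0.18 × pi.

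**The shared contrast as a carry-over test.** Compare patient sums between sequences. With the SD of the difference set to 1, the variance of a sum is (1 + rho)/(1 - rho), so SE = sqrt[(2/17)(1 + rho)/(1 - rho)] on 32 degrees of freedom.

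| rho | Power, lambda = 0.25 (half of d) | Power, lambda = 0.50 (all of d) |
|---|---|---|
| 0.3 | 8.1% | 18.0% |
| 0.5 | 6.9% | 12.9% |
| 0.7 | 6.0% | 9.1% |
| 0.9 | 5.3% | 6.2% |

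**The case against.** The best defence is that sequence may be loose, translated wording for period. Section 10.3.4 places the evaluation after four weeks within each sequence, although a sequence lasts eight weeks, and section 8.5 speaks of the product given in a sequence. Read that way, the list is treatment, period and carry-over, and nothing is duplicated. This reading is possible, but sections 1 and 10.3.3 use sequence for the randomised group. The ambiguity is itself a reason to reword.

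A second defence is that the full model belongs in the analysis plan, which is not at hand and may include period. Silence would be no finding. Here, however, the protocol names the effects, and one plain way of fitting them biases the estimate.

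Third, the trend is uncertain. Eligible patients still have symptoms despite standard therapy after at least three months of interferon, so they may be persistent cases. This stands: the losses above depend on the assumed shift, and at 0.25 SD the loss is about 2 percentage points of power.

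A reader might also infer four stronger points that the documents do not support:
- That the carry-over check has no meaning. The contrast can be computed; it cannot be attributed to carry-over rather than to a difference between the groups, and its power is low.
- That false positives rise. With balanced sequences and no carry-over term, the test becomes conservative.
- That the carry-over result decides which data are used. The protocol contains no such rule.
- That this test is the only protection against carry-over. Section 10.3.4 also places an evaluation after four weeks of treatment, which would put those placebo readings well after the last cetirizine capsule. The scores recorded during treatment, to which the second statement applies, lack that separation.

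**Conclusion.** The point holds as a defect in the stated list of effects. That carry-over and sequence are aliased once period is fitted follows from the design and needs no assumption. The cost of omitting period does need one. For shifts of 0.25 to 0.75 SD with balanced sequences, power falls from 80.7% to between about 79% and 64%, with no bias. Imbalance after drop-out adds a small bias. Only the literal three-effect fit, with carry-over confined to the cell after cetirizine, moves the whole shift into the treatment estimate.

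The power of 5-18% for detecting carry-over rests on assumed sizes and correlations. It shows that a non-significant result would reassure little, not that carry-over is present. The sample size is unaffected.

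**What to change.** In section 10.3.4, replace both statements with text to this effect: the repeated-measures ANOVA (or an equivalent mixed model) has fixed effects for treatment, period and sequence, with patient nested within sequence; the sequence contrast is aliased with carry-over, is reported descriptively only, and does not alter the primary treatment test. Use sequence for the randomised group and period for the four-week interval throughout.

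Optionally, because there is no washout, add a sensitivity analysis that leaves out the first week's injections of each period in both sequences.

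The cost is wording and one degree of freedom (power 80.8% to 80.7%). The 34 evaluable and 40 randomised patients are unchanged.

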4 STUDY OBJECTIVES

To evaluate the effectiveness of the administration of cetirizine 10 mg in improving FLS symptoms.

The primary objective of the study is the mean variation in subjective severity of the FLS, evaluated according to the patient's judgment expressed on a visual analogue scale (FLS-VAS).

The secondary objectives are: the mean variation in severity of the FLS (evaluated based on the score of FLS symptoms (Flu-Like syndrome score (FLS-S))) between the findings before the injection, 4-6 hours after the injection and 12-15 hours after the injection of IFN β during the study period; the proportion of patients with a mean reduction of \geq 2 in FLS-S; and the incidence of FLS (defined as an increase of 2 or more FLS-S points compared to the value before the injection) 4-6 hours after the injection and 12-15 hours after the injection during the study period.

The safety and tolerability of the drug will be monitored for the entire duration of the study; in particular the most common adverse reaction to cetirizine (sleepiness), will be evaluated using the Epworth Sleepiness Scale (ESS) (Johns et al., 1991), validated in Italian (Vignatelli et al., 2003), at the baseline visit (V1), at 4 (V2) and 8 (V3) weeks (or at the final study visit - Vx).

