5 STUDY PLAN

5.1 Study design and operational plan outline

A randomised, monocentric, placebo-controlled, double-blind, crossover phase IIIb pilot study.

The patients will be randomised into a period of standard therapy plus cetirizine 10 mg lasting 4 weeks followed by 4 weeks of standard therapy plus placebo, or else in the opposite sequence. If the patient is already taking drugs for the treatment of FLS, for example paracetamol or ibuprofen, they must continue to maintain the dose of that therapy as stable as possible during the study period; this is defined by the protocol as the reference standard of therapy (SOT), at the discretion of the Investigator and in accordance with standard clinical practice.

The subjective severity of the FLS shall be evaluated by the patient expressed on a visual analogue scale (FLS-VAS). The FLS-VAS scale is 10 cm in length where 0 = No discomfort due to FLS and 10 = Maximum conceivable discomfort due to FLS.

Flu-Like Syndrome symptoms (muscle pain, chills and weakness) and body temperature will be evaluated using the FLS-S score.

To calculate FLS-S, patients must assign a score to the presence and intensity of muscle pain, chills and weakness, each separately, according to the following scale: 0 = absent; 1 = minor, has not interfered with daily activities; 2 = moderate, has interfered with normal activities; 3 = severe, requiring bedrest. In addition, the patient's body temperature will be recorded to ascertain whether fever is present using the following scale: $0: <37.3^{\circ}\text{C}$; $1: \ge 37.3^{\circ}\text{C}$ and $<37.8^{\circ}\text{C}$; $2: \ge 37.8^{\circ}\text{C}$ and $<38.4^{\circ}\text{C}$; $3: \ge 38.4^{\circ}\text{C}$. The scores for individual symptoms (muscle pain, chills, weakness and body temperature) will be added together to calculate the FLS-S, which will therefore vary between 0 and 12. A change in the total score ≥ 2 points above the pre-injection score has been predefined as positive for FLS.

All scores (FLS-VAS and FLS-S) will be recorded at three distinct times for each IFN β injection: baseline (when taking the study drug, 1 hour before the injection); Time A (4 hours after the

injection) and Time B (12-15 hours after the injection). All the scores and any analgesic doses taken will be noted in the patient diary.

The patients will record the data for each injection for 8 weeks.

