8.3 Storage and delivery of the study drug

The drug will be stored in the pharmacy or in another safe place at the study centre, at a temperature below 30°C. The drug must be kept in its original packaging to protect it from direct light. One capsule of cetirizine/placebo will be administered one hour before the IFNβ injection.

At visit V1, the Investigator shall give each patient the box showing the patient's randomisation number and the words: FIRST MONTH, containing a sufficient number of capsules to cover the number of Interferon injections to be given at the highest administration frequency (14 injections/month), and shall explain the administration and storage method. At visit V2, the Investigator shall collect the unused drug and the used blister cards and give the patient the box coded with the same randomisation number and the words SECOND MONTH. When dispensing the drug packages, the Investigator shall note the date of delivery and quantity of drug dispensed in the medical record and the Case Report Form. In addition, the date and quantity of the drug provided to each patient must be recorded on an accounting form provided by the selected CRO. At visit V3 the patient must return the previously received packages to the Investigator, whether

used or not. These packages shall then be sent to the Sponsor who shall ensure that they are destroyed.

Each patient will be given a diary in which he/she must record the dates on which the drug was taken. The Investigator shall check compliance at the visits specified by the protocol.

The Investigator shall record the date the drug is returned by the patient and the number of unused capsules in the accounting form.

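### Section 10.3.4 collapses FLS incidence, an event defined per injection, into one positive/negative label per patient per treatment, by an unstated rule and with a loss of power

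*Protocol*

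**What the plan says.** The event is defined at the level of the injection. Section 4 lists as a secondary objective "the incidence of FLS (defined as an increase of 2 or more FLS-S points compared to the value before the injection", counted at 4-6 hours and at 12-15 hours over the study period. Section 5.1 has the same threshold: a change of at least 2 "points above the pre-injection score has been predefined as positive for FLS". It places the baseline reading one hour before each injection, Time A at 4 hours and Time B at 12-15 hours, and adds: "The patients will record the data for each injection for 8 weeks". Section 8.3 sizes the drug supply for injections "at the highest administration frequency (14 injections/month".

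The analysis is written at the level of the patient. Section 10.3.4 compares FLS-S with the baseline scores and continues: "The patients for whom the score is increased by 2 or more units will be defined as positive for FLS". Of these patients it says that "their frequencies will be analysed using the Armitage method, according to the crossover design". It does not say which injection, or which of the two times, decides the label.

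**The concern.** A patient can contribute up to 14 events per period at each of two times, but the planned analysis uses one yes/no per patient per treatment. Two things follow. First, the patient-level label is not the quantity that sections 4 and 5.1 define, and the step from one to the other is missing. Second, a paired binary comparison learns about treatment only from patients whose label differs between periods. A patient who goes from ten positive injections to four may carry the same label in both periods and add nothing. At stake is whether a named secondary objective can detect a reduction in FLS that the diary would show.

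**Working it through.** **The plan's own figure.** The protocol gives no power figure for FLS incidence. Its one sample size (section 10.2) is for the VAS, with d = 0.50 in units of the SD of the difference, two-sided alpha 0.05 and power 80%. By normal approximation n = ((1.960 + 0.842)/0.50)² = 31.4, so 32. With the exact noncentral t, n = 33 gives power 0.795 and n = 34 gives 0.808. The stated 34 is reproduced and does not bear on incidence.

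**Inputs.** From the protocol: a rise of at least 2, one label per patient per treatment, at most 14 injections per month, 34 evaluable patients. Assumed, because the protocol gives no values: per-injection FLS rates, 4 injections per period as a low frequency, and the spread between patients.

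**What an any-injection rule would do.** With k independent injections at per-injection rate p, P(label positive) = 1 − (1 − p)^k.

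- 0.50 vs 0.30, k = 4: 0.938 vs 0.760, difference 0.178.
- 0.50 vs 0.30, k = 14: 1.000 vs 0.993, difference 0.007.
- 0.30 vs 0.15, k = 4: difference 0.282, larger than the per-injection 0.15.
- 0.30 vs 0.15, k = 14: difference 0.096.

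Saturation under this rule therefore depends on rate and frequency. It also weakens when patients differ: with a between-patient logit SD of 2, 0.50 vs 0.30 at k = 14 gives 0.91 vs 0.84.

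**Power under several rules.** Simulation with 34 patients and 1,500 runs per setting. Labels are compared by an exact McNemar test, as a stand-in for the Armitage method that the protocol does not spell out. The proportion of positive injections is compared by a paired t test. 'Majority' means more than half of the injections are positive.

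| Rates | Injections | Logit SD | Any | One | Majority | Proportion |
|---|---|---|---|---|---|---|
| 0.50 vs 0.30 | 4 | 0 | 0.39 | 0.30 | 0.54 | 0.92 |
| | 4 | 1 | 0.30 | 0.23 | 0.45 | 0.86 |
| | 4 | 2 | 0.19 | 0.15 | 0.28 | 0.74 |
| | 14 | 0 | 0.00 | 0.30 | 0.95 | 1.00 |
| | 14 | 1 | 0.01 | 0.26 | 0.83 | 1.00 |
| | 14 | 2 | 0.06 | 0.18 | 0.41 | 1.00 |
| 0.30 vs 0.15 | 4 | 0 | 0.57 | 0.22 | 0.05 | 0.82 |
| | 4 | 1 | 0.39 | 0.18 | 0.18 | 0.79 |
| | 4 | 2 | 0.26 | 0.16 | 0.17 | 0.72 |
| | 14 | 0 | 0.11 | 0.21 | 0.00 | 1.00 |
| | 14 | 1 | 0.21 | 0.21 | 0.33 | 1.00 |
| | 14 | 2 | 0.16 | 0.15 | 0.29 | 1.00 |

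The proportion has the highest power in all 12 rows. A further simulation with 34 patients and assumed rates included a label based on a mean change of 2 or more. In one setting with 14 injections it gave 0.44, against 0.00 for any injection, 0.14 for the last injection and 0.96 for the proportion.

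**Limits.** The exact McNemar test is conservative with few discordant pairs, and the table has no extra variation within a patient between periods. Repeating the 12 settings with a mid-p test, and with such variation added, narrowed the gaps but did not change which analysis had the most power.

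**The case against.** A reader might infer that the endpoint saturates: that nearly every patient will be positive under both treatments and a real effect will be reported as none. The protocol does not support that. It states no any-injection rule. Section 10.3.4 speaks of evaluation after 4 weeks in each sequence and of mean values for the AUC, and section 4 uses mean changes for neighbouring endpoints, so a period mean or a single assessment is at least as plausible. Entry (section 6.1) requires an absolute FLS-S of at least 2, whereas positivity requires a rise of at least 2, so selection does not make most injections positive. Even under an any-injection rule, discordant pairs need not be rare. At assumed rates of 50% and 35% with 4 independent injections the labels are 0.9375 and 0.8215, and discordance is 0.9375 × 0.1785 + 0.0625 × 0.8215 = 0.22, about 7 of 34 patients. All of this stands.

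A reader might also infer that the mix of interferon products biases the result. Section 8.1 keeps interferon dose and frequency stable, so a patient's number of injections is normally the same in both periods. Under an any-injection rule frequency changes the dilution, not the fairness of the within-patient comparison.

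It can also be said that deriving the label is work for a statistical analysis plan, and that VAS and FLS-S severity are analysed anyway by repeated-measures ANOVA and AUC. The first is right about the missing rule taken alone. It does not reach the unit of analysis and the method, which the protocol itself fixes. The second lowers the stakes, because a symptom benefit would still be tested, but it does not repair the incidence objective. A well-defined patient label is legitimate; it is simply a weak use of these data.

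**Conclusion.** The concern holds in limited form. Section 10.3.4 analyses a patient label where sections 4 and 5.1 define an injection-level event at two times, and the link between them is not given. Each label examined loses power against the per-patient proportion. For 0.50 vs 0.30 a one-injection label has 0.15 to 0.30 across the settings, and it would not measure incidence over the study period. An any-injection label falls from 0.19-0.39 with 4 injections to 0.00-0.06 with 14. A majority label ranges from 0.28 to 0.95, and the proportion from 0.74 to about 1.00. These sizes rest on assumed rates, an assumed low frequency and assumed spread between patients; the direction is more secure than the numbers. Saturation, and dilution that varies with injection frequency, apply only if any single positive injection makes the patient positive. The consequence is lost power and interpretability on a secondary endpoint of a pilot trial. There is no bias in the treatment comparison and no effect on the primary VAS analysis or its 34 patients.

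**What to change.** In section 10.3.4, make the incidence analysis use every injection. For each patient and period, and separately at Time A and Time B, compute the proportion of injections with a rise of 2 or more over that injection's own pre-injection score. Analyse it in the crossover model with treatment, period, sequence and patient. An injection-level logistic mixed model with a patient effect is an equal alternative, and takes account of proportions from few injections being less precise than those from 14. The Armitage analysis of patients may stay as supportive, provided the text states which injections and which time decide the label.

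The cost is a change of analysis wording and slightly more analysis work. No new data are needed, since the diary already records each injection, and the sample size does not change.
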